2.1.7 Pharmacodynamics/genomics endpoints

PD endpoints include:

- Whole blood biomarkers: Blood eosinophil count will be measured as part of the standard clinical lab test at Visits 1 (Week -8 to -3), 3 (Week 0), 5 (Week 4), 7 (Week 8), 8 (Week 12), 9 (Week 16), 10 (Week 20), 11 (Week 24), 14 (Week 36)
- Plasma biomarkers: Eotaxin-3 measured at Visits 3 (Week 0), 5 (Week 4), 8 (Week 12), 10 (Week 20), 11 (Week 24)
- Serum biomarkers: Antigen-specific IgE, Total IgE, TARC, and periostin at Visits 3 (Week 0), 5 (Week 4), 8 (Week 12), 10 (Week 20), 11 (Week 24)
- Fractional exhaled nitric oxide: will be measured at every visit
- **ILC2 and CD34 cells and cytokines in sputum and blood** (optional; only for patients enrolled in select sites in Canada): Innate lymphoid type 2 (ILC2) cells and CD34+ cells will be measured in the blood and induced sputum. Cytokines will be assayed in the sputum and blood. At Visits 3 (Week 0) and 11 (Week 24), both sputum and blood will be collected. At Visit 14, only a sputum sample will be collected (for patients who have not entered into the long-term study).
Pharmacogenetic testing is optional and voluntary. For those patients who sign the optional pharmacogenetic informed consent form, blood samples for exploratory genetic analysis of DNA or RNA will be collected at Visit 3 (Week 0). The DNA or RNA samples may be used to determine a possible relationship between genes and response to treatment with dupilumab, possible adverse reactions to dupilumab, and to study the genetics of asthma. The DNA may be subjected to a genome-wide association study by whole genome array (common single nucleotide polymorphisms) analysis and/or to whole exome sequencing or whole genome analysis in order to thoroughly explore genetic associations with disease progression or treatment response. The RNA may be subjected to discrete panels of polymerase chain reaction (PCR) analyses, microarray analyses, or RNA sequencing analyses.

2.1.8 Health economic endpoints

A questionnaire of health care resource utilization (reliever medication, specialist visit, hospitalization, emergency or urgent medical care facility visit, outcome, sick leaves, school days' loss, etc) will be administered at each visit.

2.2 DISPOSITION OF PATIENTS

This section describes patient disposition for both patient study status and the patient analysis populations.

Screened patients are defined as any patient who signed the informed consent.

Randomized patients consist of all patients with a signed informed consent form who have had a treatment kit number allocated and recorded in the IRT database, regardless of whether the treatment kit was used.

For patient study status, the total number of patients in each of the following categories will be presented in the clinical study report using a summary table:

- Screened patients
- Screen failure patients and reasons for screen failure
- Nonrandomized but treated patients
- Randomized patients
- Randomized but not treated patients
- Randomized and treated patients
- Patients who did not complete the study treatment period as per protocol
- Patients who discontinued study treatment by main reason for permanent treatment discontinuation
- Patients who withdraw from study prior to Week 24

- Patients who withdraw from study prior to Week 24 by main reason for study discontinuation
- Patients who continued into LTS12551 study
- Status at last study contact

For all categories of patients (except for the screened and nonrandomized categories) percentages will be calculated using the number of randomized patients as the denominator. Reasons for treatment discontinuation will be supplied in tables giving numbers and percentages by treatment group. This summary will be provided by treatment group and may also be further subgrouped by region/stratum as applicable.

All critical or major deviations potentially impacting efficacy analyses, randomization, and drug-dispensing irregularities, and other major or critical deviations will be summarized in tables giving numbers and percentages of deviations by treatment group.

Additionally, the analysis populations for safety, pharmacokinetics/pharmacodynamics, and ADA will be summarized in a table by number of patients in the safety population as the denominator.

2.2.1 Randomization and drug dispensing irregularities

Randomization and drug-dispensing irregularities occur whenever:

1. A randomization is not in accordance with the protocol-defined randomization method, such as a) an ineligible patient is randomized, b) a patient is randomized based on an incorrect stratum, or c) a patient is randomized twice.

OR

2. A patient is dispensed an IMP kit not allocated by the protocol-defined randomization, such as a) a patient at any time in the study is dispensed a different treatment kit than as randomized (which may or may not contain the correct-as-randomized IMP), or b) a nonrandomized patient is treated with IMP reserved for randomized patients.

Randomization and drug-dispensing irregularities will be monitored throughout the study and reviewed on an ongoing basis.

All randomization and drug-dispensing irregularities will be documented in the IRT database. If the number of irregularities is large enough to make a tabular summary useful, the irregularities will be categorized and summarized among randomized patients (number and percentages). Nonrandomized, treated patients will be described separately.

Randomization and drug-dispensing irregularities to be prospectively identified include but are not limited to:

Randomization and drug allocation irregularities
Kit dispensation without IRT transaction
Erroneous kit dispensation
Kit not available
Randomization by error
Patient randomized twice
Stratification error
Patient switched to another site
Therapy administration without IRT transaction
Erroneous therapy administration
Therapy not available

2.3 ANALYSIS POPULATIONS

Patients treated without being randomized will not be considered randomized and will not be included in any efficacy population.

The randomized population includes any patient who has been allocated to a randomized treatment regardless of whether the treatment kit was used.

For any patient randomized more than once, only the data associated with the first randomization will be used in any analysis population. The safety experience associated with any later randomization will be assessed separately.

2.3.1 Efficacy populations

The primary efficacy analysis population will be the ITT population.

Per the OCS titration Table 2 for the treatment period, patients starting with 35mg/day at baseline cannot achieve complete (100%) reduction at Week 24. Therefore, for the analysis of the secondary endpoint, proportion of patients no longer requiring OCS at Week 24 while maintaining asthma control, the analysis population will be all the patients in the ITT population whose optimized OCS dose at baseline is less than or equal to 30mg/day.

2.3.1.1 Intent-to-treat population

The intent-to-treat (ITT) population is the randomized population analyzed according to the treatment group allocated by randomization regardless of whether the treatment kit is used or not.

2.3.2 Safety population

The safety population is defined as all patients who actually received at least 1 dose or part of a dose of the IMP, analyzed according to the treatment actually received. The safety analyses will be conducted according to the treatment patients actually received. In addition:

- Randomized patients for whom it is unclear whether they took the IMP will be included in the safety population as randomized
- For patients receiving both dupilumab and placebo during the trial, the treatment group allocation for as-treated analysis will be the dupilumab group.
- PD biomarkers will be analyzed in the safety population.

2.3.3 Pharmacokinetics population

The PK population will consist of all patients in the safety population with at least 1 evaluable functional dupilumab concentration result. Patients will be analyzed according to the treatment they actually received.

2.3.4 Anti-drug antibody population

The ADA population will consist of all patients in the safety population who had at least one reportable ADA results (either 'ADA negative' or 'ADA positive') after first dose of the study treatment.

2.4 STATISTICAL METHODS

2.4.1 Demographics and baseline characteristics

Parameters described in Section 2.1.1 will be summarized by treatment group and overall treatment groups using descriptive statistics.

Continuous data will be summarized using the number of available data, mean, standard deviation (SD), median, minimum, and maximum for each treatment group. Categorical and ordinal data will be summarized using the number and percentage of patients in each treatment group.

Parameters will be summarized on the ITT population analyzed in the treatment group to which they were randomized. Analyses for the safety population will be included in the appendices if the size of the safety population is different (>10%) from the size of that in the ITT population for any treatment group.

Medical history will be summarized by SOC and PT by treatment group and overall treatment groups. They will be first sorted by SOC using the internationally agreed order and then by the decreasing frequency of PT within each SOC in the overall treatment groups. Comorbidity medical history will be summarized separately.

No hypothesis testing on demographic and baseline characteristic data will be performed.

2.4.2 Prior or concomitant medications

The prior and concomitant medications will be presented for the randomized population.

Medications will be summarized by treatment group according to the WHO-DD dictionary, considering the first digit of the Anatomical Therapeutic Chemical (ATC) class (anatomic category) and the first 3 digits of the ATC class (therapeutic category). All ATC codes corresponding to a medication will be summarized, and patients will be counted once in each ATC category (anatomic or therapeutic) linked to the medication. Therefore patients may be counted several times for the same medication.

The table for prior medications will be sorted by decreasing frequency of ATC followed by all other therapeutic classes based on the overall incidence across treatment groups. In case of equal frequency regarding ATCs (anatomic or therapeutic categories), alphabetical order will be used.

The tables for concomitant medications will be sorted by decreasing frequency of ATC followed by all other therapeutic classes based on the incidence in the dupilumab group. In case of equal frequency regarding ATCs (anatomic or therapeutic categories), alphabetical order will be used.

Concomitant medications will be summarized for the treatment epoch and treatment emergent period separately.

Inhaled corticosteroid in combination with other controllers will be summarized separately.

Oral corticosteroids

Compliance to OCS

Compliance to the prescribed OCS dose will be calculated from Visit 3 (Week 0) until Visit 11 (Week 24) for patients who stay in the study until that time, or until the later between end of treatment and the last scheduled visit that occurred where the OCS dose adjustment is still recorded for patients who withdraw from the study before Visit 11. For each day, a patient is considered as compliant to the prescribed OCS if the patient takes the dose as prescribed. Days with missing OCS dose use record will be considered as non-compliant. Days when the ediary record of prescribed OCS dose was later corrected by the investigator (which will result in an inconsistency between the answer to the compliance question in ediary and compliance derived from comparing the actual dose to the prescribed dose) will be excluded from the compliance calculation.

Percentage of OCS compliance for a patient will be defined as the number of days that the patient was compliant divided by the total number of days during the period defined above.

Above-prescribed OCS dosing percentage for a patient will be defined as the number of days that the patient took a higher OCS dose than prescribed divided by the total number of days during the period defined above.

Under-prescribed OCS dosing percentage for a patient will be defined as the number of days that the patient took a lower dose than prescribed divided by the total number of days during the period defined above.

Missing actual OCS dose data percentage for a patient will be defined as the number of days that the patient has a missing actual dose record in ediary divided by the total number of days during the period defined above.

OCS compliance, above-prescribed and under-prescribed dosing, and missing actual OCS dose data percentages will be summarized descriptively as quantitative variables (number, mean, SD, median, minimum, and maximum). The percentage of patients whose compliance is <80% will be summarized. In addition, numbers and percentages of patients with 0, (0, 20%], and >20% above-prescribed OCS dose as well of patients with 0, (0, 20%], and >20% under-prescribed OCS dose will be summarized separately.

Inhaled corticosteroid with a second or third controller

Prior asthma controller medications will be summarized by treatment group sorted by decreasing frequency of standardized medication name based on the overall incidence across treatment groups.

Concomitant asthma controller medications at randomization will be summarized by treatment group sorted by decreasing frequency of standardized medication name based on the incidence in the dupilumab group.

If a patient takes more than one medication containing ICS, the ICS dose of different products will be standardized according to equivalent dose specified in Table 6. After conversion, the total daily dose for inhaled corticosteroid will be calculated.

Inhaled corticosteroid	Equivalent dose (mcg) to 500 mcg Fluticasone propionate (DPI or HFA)
FLUTICASONE FUROATE	100
BECLOMETASONE DIPROPIONATE (CFC)	1000
BECLOMETASONE DIPROPIONATE (HFA)	400
BUDESONIDE (DPI)	800
CICLESONIDE (HFA)	320
MOMETASONE FUROATE	440
TRIAMCINOLONE ACETONIDE	2000

Table 6 - Equivalent dose for inhaled corticosteroids for adults and adolescents (≥ 12 years)

Inhaled corticosteroid Equivalent dose (mcg) to 500 mcg Fluticasone propionate (DPI or HFA)

HFA=hydrofluoroalkane, DPI= Dry Powder Inhaler Example: A patient received 400 mcg budesonide (DPI) and 440 mcg mometasone furoate. They are equivalent to 250 mcg and 500 mcg fluticasone propionate correspondingly. The combined total daily dose is equivalent to 750 mcg fluticasone propionate and classified as high dose.

Compliance to controller medications

Compliance to the controller medication(s) with ICS component and overall compliance to all prescribed controller medications will be calculated for each patient during treatment epoch defined under Section 2.1.4. For each day, a patient is considered as compliant to the prescribed controller medication with ICS component if the actual dose of each controller medication with ICS component is same as or greater than the prescribed dose. Similarly, a patient is considered as compliant to all controller medication if the actual dose of each controller medication is same as or greater than the prescribed dose.

Compliance for controller medication(s) with ICS component is defined as the number of days when the patient is compliant to the prescribed controller medication(s) with ICS component divided by the number of days of the patient in the treatment epoch. **Overall controller medication(s) compliance** is defined as the number of days when the patient is compliant to all prescribed controller medication divided by the number of days of the patient stays in the treatment epoch. Patients are considered non-compliance for the days of missing controller medication intake data.

2.4.3 Extent of investigational medicinal product exposure and compliance

The extent of IMP exposure and compliance will be assessed and summarized by actual treatment within the safety population (Section 2.3.2).

2.4.3.1 Extent of investigational medicinal product exposure

The extent of IMP exposure will be assessed by the duration of IMP exposure.

Duration of IMP exposure is defined as last dose date – first dose date + 14 day, regardless of unplanned intermittent discontinuations (see Section 2.5.3 for calculation in case of missing or incomplete data). Duration of IMP exposure will be summarized descriptively as a quantitative variable (number, mean, SD, median, minimum, and maximum). In addition, duration of treatment exposure will also be summarized categorically by numbers and percentages for each of the following categories and cumulatively according to these categories:

- >0 and ≤ 2 weeks
- >2 and \leq 4 weeks
- >4 and ≤ 6 weeks
- >6 and \leq 8 weeks

- >8 and ≤ 12 weeks
- >12 and ≤ 16 weeks
- >16 and ≤ 20 weeks
- >20 and \leq 24 weeks
- >24 Weeks
- Additionally, the cumulative duration of treatment exposure will be provided, defined as the sum of the duration of treatment exposure for all patients, and will be expressed in patient years.

2.4.3.2 Compliance to the investigational medicinal product

A given administration will be considered noncompliant if the patient did not take the planned dose of treatment as required by the protocol. No imputation will be made for patients with missing or incomplete data.

Percentage of compliance for a patient will be defined as the number of administrations that the patient was compliant divided by the total number of administrations that the patient was planned to take during the treatment epoch defined in Section 2.1.4.

Above-planned dosing percentage for a patient will be defined as the number of administrations that the patient took a higher dose than planned divided by the total number of administrations that the patient was planned to take during the treatment epoch.

Under-planned dosing percentage for a patient will be defined as the number of administrations that the patient took a lower dose than planned divided by the total number of administrations that the patient was planned to take during the treatment epoch.

Treatment compliance, above-planned, and under-planned dosing percentages will be summarized descriptively as quantitative variables (number, mean, SD, median, minimum, and maximum). The percentage of patients whose compliance is <80% will be summarized. In addition, numbers and percentages of patients with at least 1 above-planned dose administration will also be provided, as well as numbers and percentages of patients with 0, (0, 20%], and >20% underplanned dose administrations.

Cases of overdose (at least twice the intended dose during an interval of less than 11 days) will constitute serious adverse events and will be listed as such. More generally, dosing irregularities will be listed in Section 2.2.1.

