10.4.1.2 Serious adverse event

A serious adverse event (SAE) is any untoward medical occurrence that at any dose:

- Results in death, or
- Is life-threatening, or

Note: The term "life-threatening" in the definition of "serious" refers to an event in which the patient was at risk of death at the time of the event; it does not refer to an event which hypothetically might have caused death if it were more severe.

- Requires inpatient hospitalization or prolongation of existing hospitalization, or
- Results in persistent or significant disability/incapacity, or
- Is a congenital anomaly/birth defect
- Is a medically important event
- Medical and scientific judgment should be exercised in deciding whether expedited reporting is appropriate in other situations, such as important medical events that may not be immediately life-threatening or result in death or hospitalization but may jeopardize the patient or may require medical or surgical intervention (ie, specific measures or corrective treatment) to prevent one of the other outcomes listed in the definition above.

Note: The following list of medically important events is intended to serve as a guideline for determining which condition has to be considered as a medically important event. The list is not intended to be exhaustive:

- Intensive treatment in an emergency room or at home for:
 - Allergic bronchospasm
 - Anaphylaxis (refer to Appendix K for the definition of anaphylaxis)
 - Blood dyscrasias (ie, agranulocytosis, aplastic anemia, bone marrow aplasia, myelodysplasia, pancytopenia, etc),
 - Convulsions (seizures, epilepsy, epileptic fit, absence, etc).
- Development of drug dependence or drug abuse
- ALT >3 × ULN + total bilirubin >2 × ULN or asymptomatic ALT increase >10 × ULN
- Suicide attempt or any event suggestive of suicidality
- Syncope, loss of consciousness (except if documented as a consequence of blood sampling)
- Bullous cutaneous eruptions
- Cancers diagnosed during the study

- Chronic neurodegenerative diseases (newly diagnosed)

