- An overdose (accidental or intentional) with the IMP is an event suspected by the Investigator or spontaneously notified by the patient and defined as at least twice the intended dose during an interval of less than 11 days. The circumstances (ie, accidental or intentional) should be clearly specified in the verbatim and symptoms, if any, entered on separate AE forms.
- An overdose (accidental or intentional) with any NIMP is an event suspected by the Investigator or spontaneously notified by the patient and defined as at least twice the intended dose within the intended therapeutic interval. The circumstances (ie, accidental or intentional) should be clearly specified in the verbatim and symptoms, if any, entered on separate AE forms.

Of note, asymptomatic overdose has to be reported as a standard AE.

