Table 5 summarizes the reporting timelines for select AEs and laboratory abnormalities.

Adverse event/la	Reporting timeframe	
Serious adverse ever	Within 24 hours	
Pregnancy		Within 24 hours
Overdose	Symptomatic	Within 24 hours
	Asymptomatic	Routine
ALT elevation	ALT >5 ULN if baseline ALT is ≤2 ULN	Within 24 hours
	ALT >8 ULN if baseline ALT is >2 ULN	Within 24 hours
Anaphylactic or systemic allergic reactions that are related to IMP and require treatment.		Within 24 hours
Severe injection site	Within 24 hours	
Infections as defined	Within 24 hours	

Table 5	Summary of	of adverse	event reporting	instructions
---------	------------	------------	-----------------	--------------

ALT=alanine aminotransaminase; ULN=upper limit of normal.

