- Significant elevation of alanine aminotransferase (ALT)
 - ALT >5 × upper limit of normal (ULN) in patients with baseline ALT $\leq 2 \times$ ULN; or
 - ALT >8 × ULN if baseline ALT >2 × ULN
- Pregnancy of a female subject entered in a study as well as pregnancy occurring in a female partner of a male subject entered in a study with IMP/noninvestigational medicinal product (NIMP)
 - Pregnancy occurring in a female patient entered in the clinical trial or in a female partner of a male patient entered in the clinical trial. It will be qualified as an SAE only if it fulfills 1 of the seriousness criteria.
 - In the event of pregnancy in a female participant, IMP should be discontinued.
 - Follow-up of the pregnancy in a female participant or in a female partner of a male participant is mandatory until the outcome has been determined.
- Symptomatic overdose (serious or non-serious) with IMP/NIMP
 - An overdose (accidental or intentional) with the IMP is an event suspected by the Investigator or spontaneously notified by the patient and defined as at least twice the intended dose during an interval of less than 11 days. The circumstances (ie, accidental or intentional) should be clearly specified in the verbatim and symptoms, if any, entered on separate AE forms.
 - An overdose (accidental or intentional) with any NIMP is an event suspected by the Investigator or spontaneously notified by the patient and defined as at least twice of the intended dose within the intended therapeutic interval. The circumstances (ie, accidental or intentional) should be clearly specified in the verbatim and symptoms, if any, entered on separate AE forms.

Of note, asymptomatic overdose has to be reported as a standard AE.

AESIs and other selected AE groupings will be searched based on the criteria in Table 5.

Table 5 - Criteria for adverse events of special interest and other selected AE grouping
--

AE Grouping	Criteria
AESI	
Anaphylactic reaction	Anaphylactic reaction algorithmic approach (Introductory Guide for Standardised MedDRA Queries (SMQs) Version 18.1): includes anaphylactic reaction narrow SMQ (20000021) terms; for selection based on occurrence of multiple events, the events must have occurred within 24 hours of each other

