Hypersensitivity (medically reviewed)	SMQ hypersensitivity (20000214) narrow search and [AE corrective treatment/therapy='Y' or Action taken with IMP='Drug withdrawn' or Action taken with IMP='Drug interrupted'] followed by blinded medical review (documented process) for selection of relevant systemic hypersensitivity events
Serious injection site reactions or severe injection site reactions that last longer than 24 hours	HLT = 'Injection site reaction' and either with serious status, or with severe status and (AE end date/time - AE start date/time) \ge 24 hours or ongoing
Severe or serious infection	Primary SOC = 'Infections and infestations' and with severe or serious status
Parasitic infection	Infection Type 'Parasitic' checked on eCRF Infection Defined as AESI Complementary Form
Opportunistic infection	Infection Type 'Opportunistic' checked on eCRF Infection Defined as AESI Complementary Form
Drug-related hepatic disorder	Drug-related hepatic disorders-Comprehensive search narrow SMQ (20000006)
Pregnancy	Primary SOC = 'Pregnancy, puerperium and perinatal conditions' or PT in (Aborted pregnancy, False negative pregnancy test, Pregnancy test positive, Pregnancy test urine positive, Ectopic pregnancy termination)
Symptomatic overdose with IMP	Is the event a Symptomatic Overdose with IMP? is answered Yes on AE eCRF.
Symptomatic overdose with NIMP	Is the event a Symptomatic Overdose with NIMP? is answered Yes on AE eCRF
Other selected AE grouping	
Injection site reaction	HLT = 'Injection site reaction'
Malignancy	Sub-SMQ (20000091)– Malignant or unspecified tumors
Suicidal behavior	PT in (Completed suicide, Suicidal ideation, Depression suicidal, Suicidal behavior, Suicide attempt)
Partner pregnancy	PT in (Pregnancy of partner, Miscarriage of partner)
Conjunctivitis (narrow)	PT in (Conjunctivitis, Conjunctivitis allergic, Conjunctivitis bacterial, Conjunctivitis viral, Atopic keratoconjunctivitis)

AE Grouping	Criteria
Conjunctivitis (broad)	PT in (Conjunctivitis, Conjunctivitis allergic, Conjunctivitis bacterial, Conjunctivitis viral, Atopic keratoconjunctivitis, Blepharitis, Dry eye, Eye irritation, Eye pruritus, Lacrimation increased, Eye discharge, Foreign body sensation in eyes, Photophobia, Xerophthalmia, Ocular hyperaemia, Conjunctival hyperaemia)
Hypereosinophilia	HLT = 'Eosinophilic disorders' or PT = 'Eosinophil count increased'

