- All treatment-emergent adverse events by primary SOC and PT, showing the number (%) of patients with at least 1 treatment-emergent adverse event, sorted by the internationally agreed SOC order and by decreasing incidence of PTs within each SOC.
- All treatment-emergent adverse events regardless of relationship and related to IMP by primary SOC, HLGT, HLT and PT, showing the number (%) of patients with at least 1 treatment-emergent adverse event, sorted by the internationally agreed SOC order. The other levels (HLGT, HLT, PT) will be presented in alphabetical order
- All treatment-emergent adverse events by maximal severity, presented by primary SOC and PT, showing the number (%) of patients with at least 1 treatment-emergent adverse

event by severity (ie, mild, moderate, or severe), sorted by the internationally agreed SOC order and by decreasing incidence of PTs within each SOC

- Number (%) of patients experiencing treatment-emergent adverse event(s) presented by primary and secondary SOC, HLGT, HLT, and PT sorted by the internationally agreed SOC order. The other levels (HLGT, HLT, PT) will be presented in alphabetical order
- Listing of all treatment-emergent adverse events

Analysis of all treatment emergent serious adverse event(s)

- All treatment-emergent serious adverse events by primary SOC, HLGT, HLT, and PT, showing the number (%) of patients with at least 1 serious treatment-emergent adverse event, sorted by the internationally agreed SOC order. The other levels (HLGT, HLT, PT) will be presented in alphabetical order
- All treatment-emergent serious adverse events regardless of relationship and related to IMP, by primary SOC, HLGT, HLT, and PT, showing the number (%) of patients with at least 1 treatment-emergent serious adverse event, sorted by the internationally agreed SOC order. The other levels (HLGT, HLT, PT) will be presented in alphabetical order
- All treatment-emergent serious adverse events by primary SOC and PT, showing the number (%) of patients with at least 1 treatment-emergent serious adverse event, sorted by the internationally agreed SOC order and by decreasing incidence of PTs within each SOC
- Listing of all treatment-emergent serious adverse events

Analysis of all treatment-emergent adverse event(s) leading to permanent treatment discontinuation or drug interruption

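### Two SAP labelling rules, for IMP overdose and for AESI infections, do not match the definitions they serve (minor; descriptive safety outputs only)

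*SAP*

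**What the plan says.** **Overdose.** The IMP compliance section, SAP 2.4.3.2, defines overdose as at least double the intended dose within fewer than 11 days and says that such cases "will constitute serious adverse events and will be listed as such". SAP 2.1.4.1 uses the same definition but lists "Symptomatic overdose (serious or non-serious) with IMP/NIMP" among the AESIs. Protocol 10.4.1.3 says the same and adds: "Of note, asymptomatic overdose has to be reported as a standard AE". SAP 2.1.4.1 repeats that sentence. Protocol 10.4.3 states that "Table 5 summarizes the reporting timelines for select AEs and laboratory abnormalities"; that table gives asymptomatic overdose routine reporting, against 24 hours for SAEs and for symptomatic overdose.

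**AESI infections.** SAP 2.1.4.1 and protocol 10.4.1.3 define an AESI infection by five alternative criteria: serious; needing parenteral antimicrobials; needing oral antimicrobials for more than 2 weeks; parasitic; opportunistic. Protocol 11.4.3.1.1 leaves the method of identification to the SAP, and SAP 2.1.4.1 answers that "AESIs and other selected AE groupings will be searched based on the criteria in Table 5". The general infection row of SAP Table 5 reads "Primary SOC = 'Infections and infestations' and with severe or serious status". Two further rows take parasitic and opportunistic infections from the infection type ticked on the eCRF complementary form for AESI infections.

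**The concern.** A programmer cannot satisfy both overdose statements. Followed literally, SAP 2.4.3.2 would make an asymptomatic double injection a serious event, although the protocol gives it routine reporting.

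For infections, the search is narrower than the definition in one direction and wider in another. The per-AESI summaries in SAP 2.4.5.1 (counts of TEAEs, serious events, discontinuations, intensity and outcome) are built on the groupings that this search produces. They could omit events that the SAP itself calls AESIs and include events that it does not. Infection is a safety topic that the protocol singles out in section 10.6.3, so the count should mean what its label says.

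**Working it through.** No sample size, power or alpha figure enters this point. The check is a comparison of text, plus one date difference for the side note.

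**Step 1. Overdose, same event under each rule**

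| Source | Symptomatic | Asymptomatic |
|---|---|---|
| SAP 2.4.3.2 | SAE | SAE |
| SAP 2.1.4.1 and protocol 10.4.1.3 | AESI, serious or not | Standard AE |
| Protocol Table 5 (timing) | 24 hours | Routine |

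The protocol's definition of seriousness (10.4.1.2, opening "A serious adverse event (SAE) is any untoward medical occurrence that at any dose") does not name overdose as a criterion or among its examples of medically important events. That list is not exhaustive, so an individual overdose can still be serious; it is not serious merely by being an overdose.

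Reach of the error: SAP 2.4.5.1 plans tables of serious events and a "Listing of all treatment-emergent serious adverse events", but no section derives these from dosing records. SAP Table 5 takes symptomatic overdose from a question on the AE page. The consequence is therefore at most a wrong label in a listing.

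**Step 2. Infections, criterion by criterion**

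| Criterion in the definition | Rule in SAP Table 5 |
|---|---|
| Serious | Severe-or-serious row |
| Parenteral antimicrobial | None |
| Oral antimicrobial for more than 2 weeks | None |
| Parasitic | Infection type on eCRF form |
| Opportunistic | Infection type on eCRF form |

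Three criteria have a rule and two have none (3 + 2 = 5).

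- *Omitted:* infections that meet a therapy criterion and are not serious, severe, parasitic or opportunistic. Anything serious or severe is caught by the general row, so serious and fatal infection counts do not change. The omitted events remain in the all-TEAE tables of SAP 2.4.5.1.
- *Added:* severe, non-serious infections that meet none of the other four criteria. Severity is not in the definition.

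SAP Table 5 also departs from the definition for ALT elevation, where it uses a MedDRA query. There, SAP 2.4.5.1 provides a search on laboratory values. No section does the same for the two therapy criteria.

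**Step 3. Side note on ADA**

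Inputs: target days 85 (Week 12) and 169 (Week 24) from SAP Table 10; persistence requires consecutive positives more than 84 days apart (SAP 2.1.6; protocol 9.2.5.1 says more than 12 weeks, and 12 × 7 = 84).

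169 − 85 = 84, and 84 is not more than 84.

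A patient who rolls over has no Week 36 sample (SAP 1.4). If that patient has treatment-emergent ADA, is positive at Weeks 12 and 24, and both visits fall on target, the response is not persistent. It is not indeterminate either, because the last sample is not the only positive one. It falls into the residual class, transient, without any negative post-baseline sample. A patient positive only at Week 24 is indeterminate.

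**The case against.** **The overdose sentence is a stray line in a compliance section.** The AE section, SAP Table 5 and the protocol agree with one another, and nothing feeds dosing data into the SAE tables. This stands as a limit on size. It does not remove the contradiction. A reader might infer that SAE totals would be inflated or that sites would report differently; the documents support neither, since the SAP sentence speaks only of how cases are listed.

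**The protocol delegates AESI identification to the SAP, so an analysis grouping may differ from the notification definition.** The delegation is real, and the severe-or-serious row states openly what it collects. The injection-site row is widened in a similar way. But the SAP restates the five criteria itself and then names SAP Table 5 as the search, so the mismatch is internal to the SAP.

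**The data may already be captured.** There is a dedicated eCRF form for AESI infections. Protocol 10.4.3 asks for corrective treatment with each AE, and SAP Table 5 already uses that field for hypersensitivity. This also stands: one cannot say that the information is missing, only that the written search does not use it.

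**ADA.** A reader might infer that the persistence rule is wrong and should be loosened, or that many patients would be misclassified. The documents do not support this. Protocol and SAP state the same rule, the classes are exhaustive, and positives at Weeks 12, 24 and 36 meet it (253 − 85 = 168 days). Both documents allow extra samples from early discontinuers and patients who do not roll over, and data arriving after lock go to a CSR addendum (SAP 4).

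**Conclusion.** Both mismatches hold on the text, and both are minor. SAP 2.4.3.2 contradicts SAP 2.1.4.1 and the protocol on whether an overdose is serious by definition; the effect is at most a listing label. SAP Table 5 has no rule for 2 of the 5 infection criteria and adds one category outside the definition, so the per-AESI infection summaries can under-count and over-count. The missed events are non-serious and non-severe and are reported elsewhere.

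The number of patients affected cannot be estimated: the documents give no rates of overdose, infection or ADA and no rollover share. The infection conclusion assumes that SAP Table 5 is applied as written. SAP 2.4.5 calls the safety analysis essentially descriptive, and the primary endpoint and testing hierarchy are not touched. The ADA observation is a side note confined mainly to rollover patients positive at both Weeks 12 and 24; it does not show that the definition is at fault.

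**What to change.** 1. **SAP 2.4.3.2:** delete the clause that makes overdoses serious. List overdoses with the seriousness recorded on the AE page, and reconcile the section with SAP 2.1.4.1 and protocol 10.4.1.3.
2. **SAP Table 5:** add a row for infections meeting any of the five criteria. First check whether the eCRF form for AESI infections records the two therapy criteria; the SAP shows only the parasitic and opportunistic types. If it does not, use the AE corrective-treatment field together with concomitant-medication data. Dates can give duration, but confirm that route is recorded, since protocol 8.8 names only drug and dates.
3. **SAP Table 5:** show severe non-serious infections as a separate row in the block of other selected AE groupings.
4. **ADA, optional:** keep the protocol rule and add a descriptive row for treatment-emergent patients whose last two samples are positive but do not meet it.

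The cost is SAP wording, some programming before database lock, and one check of the eCRF pages. No protocol amendment is needed, and no new patient data if the check is positive.
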